The IY-ASLD® intervention has recently been piloted within the Spanish Mental Health system (Valencia 2021). Due to the COVID-19 pandemic, the program was piloted in an online format, including all the elements of the face-to-face intervention with families and therapist connected online. Preliminary results showed that parental compliance and satisfaction with the intervention was very high (Villalta in press), and several advantages of the online format were highlighted (such as better family logistics and improved access to therapy). In view of these results, and taking into account that families of infants with genetic abnormalities are scattered all over the territory, we aim to examine the feasibility and initial effectiveness of delivering the IY-ASLD® intervention in an online format in spite of the pandemic context. It is also of note that support groups are an important resource for many families living with children with rare diseases, and it has been described that meeting via teleconference is a facilitating factor.

AIMS AND HYPOTHESIS

The main aim of the present study is to examine the feasibility and initial effectiveness of the IY-ASLD® intervention for parents of children with developmental difficulties of a genetic basis. We specifically aim to describe the compliance and satisfaction of these parents with the program, from a quantitative and qualitative perspective, and provide initial evidence on its effectiveness in terms of improving parental distress, parenting skills, as well as overall mental health difficulties in their children.

In order to achieve these goals, we designed a controlled randomized pragmatic trial where families will be randomly allocated to the intervention group (receiving the IY-ASLD® intervention online) or to the treatment as usual condition (TAU). We recruited children from the three pediatric hospitals that have a specialized unit in genetic diseases and in child mental health.

The research hypotheses are as follows:

- I. Parents' compliance with the program is acceptable (attending at least 15 of the 22 online sessions and a minimum of 50% of parents finishing the intervention).
- II. Parents report acceptable levels of satisfaction with the program.
- III. Parents who received the intervention present reduced levels of parental stress when compared to the control group.
- IV. Parents who received the intervention show reduced levels of depressive symptoms and expressed

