- emotions when compared to the control group.
- V. Parents who received the intervention present an increase in their positive parenting skills when compared to the control group.
 - VI. Parents who received the intervention report a decrease in the levels of children's externalizing and internalizing symptoms when compared to the control group.

METHODOLOGY

The GAP project will be implemented in three Pediatric Hospitals (Hospital Sant Joan de Déu in Barcelona, Hospital Vall d'Hebron in Barcelona, Hospital Parc Taulí in Sabadell). Participating families will be recruited from specialist paediatric genetic units within each hospital, and will be randomly allocated to the TAU condition or to the intervention group. Clinical psychologists and child psychiatrists working in specialised mental health services for neurodevelopmental disorders within the hospitals will deliver the intervention. Before the intervention takes place, between 4 and 8 focus groups will be carried out with a subsample of families to explore their needs, challenges, preferences and expectations. After the intervention, interviews will be conducted with parents of the intervention group and with clinicians who delivered the intervention.

A mixed-methods approach will be used, considering the benefits of combining quantitative and qualitative methods in health psychology clinical trials (Bishop 2015).

Sample size:

For the sample size calculation, we used the outcome parental stress, measured through the questionnaire Parental Stress Index Short Form (PSI-SF). This is a 36-item scale, with a range of 180 points. There is data showing that a decrease of 16.5 points in the total scale stress score can be seen after attending an IY program. Given that this study will be conducted with parents of children presenting neurodevelopmental difficulties, we anticipated that the decrease in the PSI-SF score would be lower. We estimated the necessary sample size considering a power of 80%, $\alpha = 0.05$, a difference between pre- and post-test of 10 points, and a standard deviation of 20, using a paired-samples t test. We estimated 34 participants needed per arm of the study. Thus, we aim to recruit approximately participants. The drop-out rate has not been included when calculating the sample size, considering that a sample of 68 participants is similar than previous studies and in line with recommendations by the National Institute of Health Research.

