For the focus groups that will be conducted before the intervention, each group will have between 4 and 6 participants (mothers or fathers), considering the recommendations provided by Tausch & Menold (2016). Taking into account potential drop-outs, 6 parents will be contacted per focus group.

For the post-intervention individual interviews with parents, parents will be selected from the 4 intervention groups conducted in the 3 sites: a minimum of 2 parents per group will be interviewed, therefore at least 8 interviews will be conducted. Parents who dropped out of the study will also be invited to participate to explore their experiences. Data saturation will be used to determine the final sample size.

For the post-intervention individual interviews with clinicians, all clinicians that delivered the intervention will be interviewed after the intervention phase.

Eligibility criteria:

The following are the inclusion criteria:

1. Children aged 3.0 – 7.11 years at recruitment
2. Children with a diagnosis or in diagnostic process for high suspicion of a genetic abnormality
3. For children up to 5.11 years with withdrawn (defined as CBCL/1.5-5 scores above the borderline clinical range, T-score > 65) AND/OR pervasive developmental problems (defined as CBCL/1.5-5 scores above the borderline clinical range, T-score > 65) AND/OR socialization difficulties (defined as Vineland-III scores below 1SD in the socialization subdomains).
4. For children over 6 years with social problems (defined as CBCL/6-18 scores above the borderline clinical range, T-score > 65) AND/OR thought problems (defined as CBCL/6-18 scores above the borderline clinical range, T-score > 65) AND/OR socialization difficulties (defined as Vineland-III scores below 1SD in the socialization subdomains).
5. Parents/caregivers showing good understanding of the Spanish or Catalan language
6. Parents/caregivers consenting to take part in the study and signing the informed consent

The following are the exclusion criteria:

1. Children diagnosed with an Autism Spectrum Disorder
2. Children scoring above diagnostic cut-off for Autism or Autism Spectrum Disorder in the ADOS-2.
3. Attending another structured parenting program
4. Children in the care of their local authority

Recruitment:

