The IY-ASLD® program is a 14-session group-based intervention for parents of children presenting neurodevelopmental difficulties. During the COVID-19 pandemic, the Incredible Years developers adapted the intervention to be performed online (22 sessions approximately). Each online group will include approximately 6-10 participants. The intervention includes video modelling and emphasizes the importance of practice-based learning through role-playing. Weekly home tasks will be assigned to parents, and families will be phoned each week to encourage home-based practice. Fidelity to the treatment manual will be ensured in different ways. Group interventions will be conducted by experienced psychiatrists and clinical psychologists, officially trained in the IY-ASLD® model and its online adaptation by an accredited trainer. Group leaders will complete weekly fidelity checklists and will be supervised by certified supervisors throughout the intervention. The TAU condition involves outpatient appointments with neuropsychiatrists to monitor children's developmental level and drug prescription when needed. All infants are also treated in Early Years Centers based in the community, where they receive individual unstructured interventions to foster children's development. Families allocated to the intervention group will also receive TAU.

Measures:

Baseline and sample descriptors:

Sociodemographic and child clinical variables will be collected from clinical notes and parent reports. Socioeconomic status will be determined using Hollingdale's Index of Social Position.

The following questionnaires will be administered:

- Social Communication Questionnaire (SCQ): it is a 40-item parent report measure, yes/no format, based on the Autism Diagnostic Interview-Revised (ADI-R). The Lifetime version of this questionnaire will be administered before the intervention to describe children's social communication difficulties. It is a robust tool that has shown good validity, and it has been widely adopted by both the research and clinical community.

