Data will be collected at baseline (before performing randomization) and after finishing the IY-ASLD® intervention. Parents consenting to participate will be offered a hospital appointment before the intervention with a research assistant to evaluate inclusion criteria (parental questionnaires and ADOS). If they meet inclusion criteria they will then be contacted on the phone to complete the baseline assessment (including self-report measures, children outcome measures, and a voice recording for the ASFMSS tool). If both parents participate in the study, they will fill out the children's outcome measures together (by consensus) and the parental outcome measures individually.

Qualitative data collection:

Qualitative data will be collected at baseline (focus groups) and after finishing the IY-ASLD® intervention (interviews). Parents included in the study will be contacted on the phone to be invited to participate in an online focus group. We will aim for a representative sample in terms of children's diagnosis, age, gender

and cognitive status (according to DP-3 cognitive subscale score). If a parent declines to participate in a focus group, another parent will be contacted until 6 individuals per focus group are recruited. The focus groups will be delivered online and will be conducted by a psychologist trained in qualitative methods, external to the clinical team, and they will be audio-recorded and transcribed verbatim.

The same psychologist will conduct the individual interviews to parents and clinicians, which will have an online format and will be audio-recorded and transcribed verbatim.

SCIENTIFIC AND SOCIAL INTEREST

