This scientific gap is also worrying from a societal point of view. Families whose infants are diagnosed with a genetic abnormality face high stress levels related to parenting children with behavior, communication and social difficulties, and in relation to how the diagnosis will affect their children's mental health. In this regards, parents tend to look for peer-to-peer support in family associations. The GAP project will bring families with similar problems closer, creating opportunities for peer-to-peer support while providing rigorous and specialized treatment options to improve parent and children mental health.

Finally, The GAP study represents a scientific and clinical challenge as it involves the collaboration between the three hospitals with specialized mental health and genetic diseases units within our public health system. The collaborative approach of the current project is set not only for recruitment purposes, but also for implementation of joint treatment strategies, as patients will be allocated to one of the online intervention groups according to their clinical profile, and not according to the recruitment site. The design of this project goes beyond health institutions catchment areas, brings together centers for child development and children mental health, and integrates physical and mental health with the ultimate aim of providing the best possible assistance to this often overlooked group of infants.

REFERENCES

- Ae, L. A. O., Mchugh, L., Jo, A. E., Ae, S., & Reed, P. (2007). Parenting Stress Reduces the Effectiveness of Early Teaching Interventions for Autistic Spectrum Disorders. <http://doi.org/10.1007/s10803-007-0497-7>
- Bishop, F. (2015). Using mixed methods research designs in health psychology: an illustrative discussion from a pragmatist perspective. *British Journal of Health Psychology*, *20*(1), 5-20. <https://doi.org/10.1111/bjhp.12122>

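### The 80% power for 34 per arm is a within-arm, pre-post figure for independent observations; for the between-arm stress comparison it is about 54%, and somewhat less if outcomes correlate within the four online groups

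*Protocol*

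**What the plan says.** The Protocol's Sample size section sizes the trial on the PSI-SF total score. Its inputs are 80% power, alpha 0.05, a pre-post difference of 10 points and "a standard deviation of 20, using a paired-samples t test". It concludes: "We estimated 34 participants needed per arm of the study". No intra-group correlation or design effect is mentioned, and drop-out is expressly left out.

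The question to be answered is hypothesis III in Aims and Hypothesis: "Parents who received the intervention present reduced levels of parental stress when compared to the control group". The same section says that "families will be randomly allocated to the intervention group" or to treatment as usual (TAU).

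Delivery is in groups. The Intervention section says "Each online group will include approximately 6-10 participants", and the interview part of the Sample size section says "parents will be selected from the 4 intervention groups conducted in the 3 sites". TAU is described as outpatient appointments and individual community interventions, so it is not grouped.

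On who supplies scores, the Data collection section says that when both parents take part they complete the children's "outcome measures together (by consensus) and the parental outcome measures individually".

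**The concern.** A sample-size statement should give the power of the comparison that the trial will make. This one gives the power to detect change from baseline in a single arm, as if every observation were independent. The trial's stress hypothesis needs the difference between two arms, whose variance is the sum of both arms' variances. In addition, parents treated together share leaders, role-play and peer contact, which can make their outcomes correlate and widen the variance of the intervention mean.

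At stake is how a PSI-SF result is read. A non-significant difference between arms could be taken as evidence of no effect because the trial claimed 80% power, when its power for that comparison was well short of 80%.

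**Working it through.** **Inputs from the Protocol.** Difference 10 points, SD 20, alpha 0.05, 34 per arm (Sample size); four intervention groups (interview part of Sample size), so the mean group size is m = 34/4 = 8.5, within the 6 to 10 given under Intervention.

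**Assumptions.** The test is two-sided. SD 20 is the SD of change in each arm. The between-arm difference is the full 10 points, that is, no mean change under TAU. The intra-group correlation (ICC) is 0.01, 0.05 or 0.10, in the intervention arm only; the Protocol gives no value.

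**1. The Protocol's own figure.** Paired t test with d = 10/20 = 0.5, noncentral t: n = 34 gives 80.8% and n = 33 gives 79.5%. So 34 reproduces as the minimum for 80%, with 20 read as the SD of the differences. A one-sided test would have needed only 27.

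**2. Between arms, no clustering.** SE = 20 × √(1/34 + 1/34) = 4.85. Power = Φ(10/4.85 − 1.96) = Φ(0.10) = 54.0%; the t test on 66 df gives 52.9%. For 80% power the same inputs would need 63 per arm (normal) or 64 (t test). The difference detectable with 80% power at 34 per arm is 2.80 × 4.85 = 13.6 points.

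**3. With baseline adjustment.** If pre and post variances are equal and the pre-post correlation is r, the residual variance is 20² × (1 + r)/2.
- r = 0.5: variance 300, SE 4.20, power Φ(10/4.20 − 1.96) = 66%.
- r = 0.8: variance 360, SE 4.60, power Φ(10/4.60 − 1.96) = 58%.

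The values of r are assumptions.

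**4. Adding clustering in the intervention arm (unadjusted).** Design effect DE = 1 + (8.5 − 1) × ICC, and SE = 20 × √(DE/34 + 1/34).

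| ICC | DE | SE | Power, normal | Power, t (66 df) | Detectable difference at 80% |
|---|---|---|---|---|---|
| 0 | 1 | 4.85 | 54.0% | 52.9% | 13.6 |
| 0.01 | 1.075 | 4.94 | 52.6% | 51.4% | 13.8 |
| 0.05 | 1.375 | 5.29 | 47.3% | 46.2% | 14.8 |
| 0.10 | 1.75 | 5.69 | 42.0% | 41.0% | 15.9 |

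**5. Splitting the shortfall.** Moving from the paired test to the between-arm comparison costs 80.8 − 54.0, about 27 points. Clustering then costs a further 54.0 − 52.6, 54.0 − 47.3 and 54.0 − 42.0, about 1, 7 and 12 points.

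**6. Slack in the paired figure.** Interpolating between n = 33 (79.5%) and n = 34 (80.8%), power reaches 80% at an effective n of about 33.37. That is DE = 34/33.37 = 1.019, or ICC = 0.019/7.5, about 0.0025. At ICC 0.01, 0.05 and 0.10 the effective n is 31.6, 24.7 and 19.4, and paired power is about 78%, 66-68% and 55-57%, depending on the degrees of freedom used.

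**The case against.** The strongest reply is that clustering is a minor matter here. Most of the shortfall comes from the choice of test, every clustering figure rests on an assumed ICC, and at 0.01 the loss is about one point. That stands, and it sets the order of the two causes. The 54% is also conditional: it assumes an unadjusted comparison of change, and baseline adjustment would do better, as step 3 shows. Even so, the adjusted figures remain below 80%. Finally, feasibility is primary, PSI-SF is secondary, and the Protocol claims only initial effectiveness and also supports 68 by similarity to previous studies. This limits the consequence but does not make the stated power correct.

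Several stronger readings are tempting and are not supported:
- A reader might infer that any positive group correlation takes the paired figure below 80%. It does so only above an ICC of about 0.0025.
- A reader might cite the statement that "patients will be allocated to one of the online intervention groups according to their clinical profile" as a further source of lost power. Sorting families who were already randomised into groups by a baseline characteristic leaves the arm mean, and hence its variance, unchanged. Only effects arising from treatment in a shared group cost power.
- A reader might infer that the unit of N is undefined, because two parents of one family can each give PSI-SF scores. The sizing sentence is loose, but the opening summary (about 68 children) and the randomisation of families in Aims and Hypothesis and in Randomization point to 34 families per arm.
- A reader might infer an inflated type I error. That would depend on an analysis that ignores groups or families, and the Protocol specifies no such analysis.

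**Conclusion.** The concern holds in a limited form. The stated 80% is correct arithmetic for a question that the trial's stress hypothesis does not ask. For the between-arm comparison, 34 per arm gives about 53-54% power unadjusted and about 58-66% with baseline adjustment at an assumed pre-post correlation of 0.8 to 0.5. Group correlation in the intervention arm lowers the unadjusted figure to about 53%, 47% or 42% at assumed ICCs of 0.01, 0.05 and 0.10. The paired-test mismatch is the main cause and clustering is secondary.

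These figures assume 34 analysed families per arm, an SD of change of 20 in both arms and no mean change under TAU. Drop-out, or improvement under TAU, would lower them. The detectable difference of 13.6 to 15.9 points is larger than the 10 points that the Protocol anticipates.

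**What to change.** In the Sample size section, replace the paired-test statement with the power, or the detectable difference, for the between-arm comparison with 34 per arm. Say whether baseline adjustment is assumed and what the SD of 20 refers to. Give the result over a stated ICC range applied to the intervention arm only; on the inputs above, unadjusted, the detectable difference is 13.6 points without clustering and 13.8, 14.8 or 15.9 with it. State in the same place that N counts families.

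This costs a few sentences and a less favourable stated power. No extra families are needed, since the aim is feasibility and initial effectiveness. How two parents' scores from one family are combined, and how group clustering is handled in the analysis, can be left to the SAP.

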Parents will be recruited from the three specialist units in paediatric genetic abnormalities within the three Hospitals. A leaflet with the inclusion and exclusion criteria will be handed out to clinicians working in the services. Clinicians will discuss the study with eligible families and will ask the families permission to be contacted by the study researchers. If they agree to be contacted about the project, a research assistant will call the family to discuss the study further. If the family is interested in participating in the study the researcher will set up an appointment to evaluate all the inclusion criteria (including the Autism Diagnostic Observation Schedule-ADOS-). During this visit, researchers will make sure that participants receive all the necessary information and have the opportunity to ask any questions. If participants meet the inclusion criteria, parents will be asked to sign the informed consent and to complete the pre-intervention assessment. Any children excluded from the study due to scoring above diagnostic cut-off for ASD (ADOS) will be referred to specialised assessment within the mental health public system. Participants will be able to discontinue the treatment sessions or drop out from the control group at any point at their request. The participation in the study will not affect their usual treatment.

Randomization:

Randomization will take place once all the participating families have completed baseline measures. They will be randomly allocated to the intervention group or to the TAU condition. An independent researcher will carry out the randomization process, and researchers who are responsible for patient recruitment or intervention delivery will not be involved. Due to the pragmatic and clinically focused nature of the study, further blinding procedures will not be possible.

Intervention:

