Feasibility outcomes (primary outcomes):

- Parents' engagement with the program and participant retention: parents' attendance at the sessions will be monitored throughout the intervention, expecting they will attend at least 15/22 sessions with a minimum of 50% of parents finishing the program.
- Compliance and satisfaction throughout the study: the questionnaire Autism Program Parent Weekly Evaluation is part of the IY-ASLD® program materials and will be administered after each session to collect information regarding compliance and satisfaction throughout the study.
- Parents' acceptability and satisfaction with the program: this outcome will be evaluated quantitatively and qualitatively. From a quantitative perspective, parents' overall acceptability and satisfaction with the program will be assessed with the Autism Program Parent Final Satisfaction Questionnaire (included within the IY-ASLD® program). Data will be collected after the last session. From a qualitative perspective, individual interviews will be conducted after the last session of the intervention to explore parents' acceptability, satisfaction and overall experience with the intervention.

Effectiveness outcomes (secondary outcomes):

- Parental stress will be measured with the Parent Stress Inventory-Short Form (PSI-SF). This is a 36-item questionnaire that specifically focuses on assessing parental stress associated with the care of their offspring. It has three domains: parental distress, parent-child dysfunctional interaction, and difficult child, which combine to form a total stress scale. This tool will be administered before and after the intervention. It has shown good internal consistency.
- Parents' depressive symptoms will be measured using the Beck Depression Inventory (BDI). The BDI is a 21-item screening tool assessing the severity of depressive symptoms. It is a standardized and validated questionnaire, often used in mood disorder assessments. It will be collected before and after the intervention. It has good reliability.

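### The 80% power for parental stress belongs to a within-arm paired test with no drop-out; the between-arm comparison in hypothesis III has about 53% if SD 20 is the SD of change

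*Protocol*

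**What the plan says.** Under METHODOLOGY, Sample size, the protocol sizes the trial on the PSI-SF total score at 80% power and alpha 0.05, with "a difference between pre- and post-test of 10 points, and a standard deviation of 20, using a paired-samples t test". The result is 34 per arm, and the target is about 68. On loss it says: "The drop-out rate has not been included when calculating the sample size". The reason given is that 68 resembles earlier studies and agrees with a research body's recommendation.

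The hypothesis that this outcome serves is number III under AIMS AND HYPOTHESIS: "Parents who received the intervention present reduced levels of parental stress when compared to the control group". The Outcomes section lists the PSI-SF as a secondary (effectiveness) outcome; the primary outcomes concern feasibility.

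Three other places bear on loss:
- Recruitment: "Participants will be able to discontinue the treatment sessions or drop out from the control group at any point at their request".
- Sample size, on the interviews: "Parents who dropped out of the study will also be invited to participate to explore their experiences".
- Outcomes, on the final satisfaction questionnaire: "Data will be collected after the last session".

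Data collection dates the post-test from the end of the intervention, gives no calendar window, and has both parents answer the parental measures separately when both take part.

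**The concern.** A paired t test asks whether scores in one arm change over time. A randomised comparison asks whether the change differs between arms, and it carries the sampling error of both. The 80% therefore cannot be carried over to hypothesis III. Nor does resemblance to earlier studies support it under loss: that may justify the size of a feasibility trial, but it does not bear on power.

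The stake is interpretation. A non-significant parental-stress comparison would be read against 80%, when on the plan's own figures the chance of detecting a 10-point difference may be nearer one half.

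**Working it through.** **Inputs from the protocol (Sample size).** Difference 10, SD 20, alpha 0.05, 34 per arm. Sidedness is not stated; a two-sided exact test is used because it reproduces the 34.

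**Assumptions, because the protocol gives no figures.** Retention of 31 and 27 per arm (34 × 0.9 = 30.6; 34 × 0.8 = 27.2); pre/post correlation r of 0.5 or 0.7; one PSI-SF pair per family.

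**Step 1: the plan's own figure.** Paired t test, noncentrality (10/20)·√n, n − 1 degrees of freedom.
- n = 34: 0.5 × √34 = 2.92, power 80.8%
- n = 33: 0.5 × √33 = 2.87, power 79.5%
- n = 31: 76.9%; n = 27: 70.6%

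So 34 is the smallest n that reaches 80%, and the stated figure is reproduced.

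**Step 2: between arms, SD 20 as the SD of change.** Two-sample t test on change, noncentrality (10/20)·√(n/2), 2n − 2 degrees of freedom.

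| Per arm | Noncentrality | Power for 10 points | Detectable difference at 80% |
|---|---|---|---|
| 34 | 2.06 | 52.9% | 13.8 |
| 31 | 1.97 | 49.1% | 14.5 |
| 27 | 1.84 | 43.8% | 15.5 |

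**Step 3: between arms, SD 20 as the SD of scores, baseline adjusted.** Residual SD = 20·√(1 − r²), which is 17.3 at r = 0.5 and 14.3 at r = 0.7; 2n − 3 degrees of freedom.

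| Per arm | r = 0.5 | r = 0.7 |
|---|---|---|
| 34 | 65% | 81% |
| 31 | 61% | 77% |
| 27 | 55% | 71% |

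At r = 0.7, 33 per arm already falls just short of 80%.

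**Step 4: how the two readings relate.** If 20 is the SD of scores, the SD of change is 20·√(2(1 − r)). That is 20 at r = 0.5, so there the readings agree and baseline adjustment alone lifts 53% to 65%. At r = 0.7 it is 20·√0.6 = 15.5, which is not the 20 that yields 34 pairs. The favourable column therefore applies only if a score SD was entered where the paired test needs a change SD. A higher correlation would help further on that reading: at r = 0.8 the residual SD is 20·√0.36 = 12, and power is 92%, 90% and 85% at 34, 31 and 27.

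**Step 5: where the shortfall comes from.** Under the change-SD reading, moving from the within-arm to the between-arm test costs 80.8 − 52.9 = 27.9 percentage points with no loss at all. Loss then costs 52.9 − 49.1 = 3.8 points at about 10% and 52.9 − 43.8 = 9.1 points at about 20%.

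**The case against.** Five points can be made for the plan.

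- **The zero allowance is disclosed, and one lost pair matters little.** This stands. The fall from 80.8% to 79.5% is trivial, and nothing is hidden.
- **The PSI-SF is secondary in a feasibility trial, retention is itself a primary outcome, and the online pilot was encouraging ("Preliminary results showed that parental compliance and satisfaction with the intervention was very high").** This stands as a limit on weight. It does not make the 80% apply to the between-arm comparison.
- **Both parents may answer, so pairs may outnumber families.** This stands as a caveat. As an illustration, take 31 families per arm, half with two parents and a within-family correlation of 0.5. A two-parent family then counts as 2/1.5 = 1.33, giving 15.5 + 15.5 × 1.33 ≈ 36 effective pairs, about 83% on the paired test. The between-arm test of Step 2 would need 64 per arm for 80%.
- **The analysis model may sit in an SAP that is not shown, and adjustment could bring power to 80%.** It could, but only on the score-SD reading with a high correlation, and the protocol states neither.
- **Nothing ties the post-test to attendance.** This stands. TAU families never finish the programme, so its end reads naturally as one trial time point. The protocol also words stopping sessions differently from dropping out.

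A reader might infer a completers-only post-test and satisfaction score, because the interview is the only stated contact with parents who dropped out. The text is silent on this and does not plan it. A reader might also take the feasibility threshold ("with a minimum of 50% of parents finishing the program") as expected loss, which would leave 17 pairs and 49.1% power on the paired test. It is a criterion for acceptable compliance and forecasts nothing about missing post-tests.

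**Conclusion.** Wrong as written, in a limited sense. The arithmetic behind 34 is correct, but the 80% is for a within-arm test on complete pairs, while hypothesis III compares arms.

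With SD 20 as the SD of change, the reading that the paired test implies, power for an unadjusted comparison of change is about 53%, falling to 49% and 44% at the assumed retention levels. With SD 20 as the SD of scores and baseline adjusted for, it runs from 55% to 81% over correlations of 0.5 to 0.7. Within that range, 80% is reached only at the upper end and with almost no loss. These figures rest on two-sided 5% tests, one PSI-SF pair per family, and assumed retention and correlation.

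It would go too far to say that the missing drop-out allowance is what breaks the power, or that the trial must be enlarged. Attrition is the smaller part of the shortfall, and a feasibility trial may reasonably keep 68. Silence about parents who stop sessions calls for a clarification and is not an error in the plan.

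**What to change.** **Main change, Sample size section.** Keep the recruitment target.
1. Label the 80% as power for a within-arm pre/post test with 34 complete pairs.
2. Say whether SD 20 is the SD of change or of scores.
3. Replace the drop-out sentence with between-arm power or detectable difference for the PSI-SF, named as a secondary outcome, at stated retention levels.

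If SD 20 is the SD of change, the text could read: *For a 10-point difference between arms in PSI-SF change (SD 20, two-sided 5% test), 34, 31 and 27 families per arm give about 53%, 49% and 44% power; the differences detectable with 80% power are 13.8, 14.5 and 15.5 points.* If it is the SD of scores, give the baseline-adjusted figures together with the assumed correlation. State how families with two responding parents are counted.

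**Minor clarification, Data collection and Outcomes.** State that the post-test is collected in one window for both arms, dated from the last scheduled group session. State also that the post-test (all randomised families) and the final satisfaction questionnaire (intervention-arm parents) are sought whatever the attendance, unless the family withdraws from data collection. This belongs in the protocol because a later SAP cannot recover data that were never collected.

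**Cost.** A less favourable stated power, and some phone or online contact with parents who stopped sessions. The protocol already plans to contact those who dropped out for interviews.
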